8.3 Premature termination or suspension of the study

The sponsor reserves the right to terminate the study at any time globally or locally. Investigators can terminate the participation of their site in the study at any time.

If a study is prematurely suspended or terminated, the sponsor will promptly inform the investigators, the IECs/IRBs, and health authorities, as appropriate, and provide the reasons for the suspension or termination.

If the study is suspended or prematurely terminated for any reason, the investigator — in agreement with the sponsor — must promptly inform all enrolled subjects and ensure their appropriate treatment and follow-up, as described in Section 8.4. The sponsor may inform the investigator of additional procedures to be followed in order to ensure that adequate consideration is given to the protection of the subjects' interests.

In addition, if the investigator suspends or terminates a study without prior agreement from the sponsor, the investigator must promptly inform the sponsor personnel and the IEC/IRB, and provide both with a detailed written explanation of the termination or suspension.

If the IEC/IRB suspends or terminates its approval / favorable opinion of a study, the investigator must promptly notify the sponsor personnel and provide a detailed written explanation of the termination or suspension.

8.4 Medical care of subjects after study completion / withdrawal from study

After the subject's study completion or premature withdrawal from the study, whichever applies, the investigator/delegate will explain to subjects what treatment(s) / medical care is necessary and available according to local medical practice and applicable guidelines. Such care may include:

- Use of drugs which were forbidden during concomitant study treatment administration;
- Enrollment in the OLE of this study conducted under a separate protocol, only for those subjects who have completed the 6-month double-blind treatment period, providing they fulfill the specific eligibility criteria of this separate study.

Female subjects of childbearing potential and fertile male subjects will be reminded of the contraception requirements as described in Section 4.5 and 4.6, respectively.

9 SAFETY DEFINITIONS AND REPORTING REQUIREMENTS

9.1 Safety definitions

9.1.1 Definition of adverse events

An AE is any untoward medical occurrence, i.e., any unfavorable and unintended sign, including an abnormal laboratory finding, symptom, or disease that occurs in a subject

during the course of the study, whether or not considered by the investigator as related to study treatment.

AEs include:

- Exacerbation of a pre-existing disease if considered medically relevant. The evolution of the FD disease condition including worsening of symptoms (e.g., neuropathic pain, GI symptoms) will be evaluated and reported as AE only if considered medically significant based on investigator judgment;
- Increase in frequency or intensity of a pre-existing episodic disease or medical condition;
- Disease or medical condition detected or diagnosed during the course of the study even though it may have been present prior to the start of the study;
- Continuous persistent disease or symptoms present at study start that worsen following the signing of the ICF;
- Abnormal change on physical examination, ECG findings, if they represent a clinically significant finding that was not present at study start or worsened during the course of the study as per investigator medical assessment;
- Laboratory test abnormalities if they represent a clinically significant finding (symptomatic or not) which was not present at study start or worsened during the course of the study as per investigator judgment, led to dose reduction, interruption or permanent discontinuation of study treatment.

9.1.2 Definition of serious adverse events

An SAE is defined by the ICH guidelines as any AE fulfilling at least 1 of the following criteria:

- Fatal;
- Life-threatening: refers to an event in which the subject was at risk of death at the time of the event. It does not refer to an event that hypothetically might have caused death had it been more severe;
- Requiring in-patient hospitalization or prolongation of existing hospitalization;
- Resulting in persistent or significant disability or incapacity;
- Congenital anomaly or birth defect;
- Medically significant: refers to important medical events that may not immediately result in death, be life-threatening, or require hospitalization but may be considered medically significant based upon appropriate medical judgment, as they may jeopardize the subject, and/or may require medical or surgical intervention to prevent one of the outcomes listed in the definitions above.

The following reasons for hospitalization are not considered as SAEs:

- Hospitalization for cosmetic elective surgery, or social and/or convenience reasons;
- Hospitalization for pre-planned (i.e., planned prior to signing ICF) surgery or standard monitoring of a pre-existing disease or medical condition that did not worsen, e.g., hospitalization for coronary angiography in a subject with stable angina pectoris.

However, complications that occur during hospitalization are AEs or SAEs (e.g., if a complication prolongs hospitalization).

9.1.3 Definition of suspected unexpected serious adverse reactions

The expectedness of an SAE is determined by the sponsor according to the reference safety information (RSI) section provided in the most recent version of the IB.

Any SAE that is assessed as related and unexpected against the RSI is known as a SUSAR.

9.1.4 Intensity of adverse events

The intensity of AEs is graded on a three-point scale — mild, moderate, severe — as follows:

□ Mild

The event may be noticeable to the subject. It does not usually influence daily activities, and normally does not require intervention.

□ Moderate

The event may make the subject uncomfortable. Performance of daily activities may be influenced, and intervention may be needed.

□ Severe

The event may cause noticeable discomfort and usually interferes with daily activities. The subject may not be able to continue in the study, and treatment or intervention is usually needed.

A mild, moderate, or severe AE may or may not be serious [see Section 9.1.2]. These terms are used to describe the intensity of a specific event. Medical judgment should be used on a case-by-case basis.

Seriousness, rather than intensity assessment, determines the regulatory reporting obligations [see Section 9.3.2].

9.1.5 Relationship to study treatment

Each AE/SAE must be assessed by the investigator as to whether or not there is a reasonable possibility of causal relationship to the study treatment, and reported as either related or unrelated.

9.1.6 Relationship to protocol-mandated procedure

An AE/SAE is defined as related to protocol-mandated procedure if it appears to have a reasonable possibility of a causal relationship to either the study design or to a protocol-mandated procedure.

The determination of the likelihood that a protocol mandated procedure caused the AE/SAE will be provided by the investigator.

9.2 Time period and frequency for adverse event / serious adverse event assessment and follow-up

The occurrence of an AE/SAE may come to the attention of study personnel during study visits, telephone calls or interviews of study participants presenting for medical care.

At each study visit (scheduled or unscheduled), the investigator will inquire about the occurrence of AE/SAEs since the last visit.

9.2.1 Follow-up of adverse events

AEs still ongoing at the EOS visit must be followed up until resolution, are no longer considered clinically relevant or until stabilization.

9.2.2 Follow-up of serious adverse events

SAEs still ongoing at the EOS visit must be followed up until resolution, stabilization, or until the event outcome is provided.

9.3 Reporting procedures

9.3.1 Reporting of adverse events

All AEs with an onset date after signing of the ICF and up to 30 days after study treatment discontinuation or up to the last visit of the PTOP period (whichever is the latest) must be recorded on specific AE forms of the eCRF.

Information to be collected in an AE form in the eCRF includes date of onset, action taken with the study treatment, outcome of AE, date of resolution (if applicable) and PI's assessment of intensity, and relationship to study treatment, study design or protocol mandated procedures.

Information on worsening of intensity will be collected on a new AE form. If the AE lessens in intensity, no change in the severity is required to be reported.

Follow-up information on ongoing AE obtained after the subject's EOS visit will not be collected in the eCRF.

9.3.2 Additional reporting procedure for serious adverse events

All SAEs must be reported by the investigator to the sponsor's Global Drug Safety department within 24 hours of the investigator's first knowledge of the event.

All SAEs occurring after signing of the ICF up to 30 days after study treatment discontinuation or up to the last visit of the PTOp period (whichever is the latest) must be recorded on an SAE form, regardless of the investigator-attributed causal relationship with study treatment or study-mandated procedures.

The SAE forms must be sent to the sponsor's Global Drug Safety department (see contact details on the SAE form). The investigator must complete the SAE form in English, and must assess the event's causal relationship to the study treatment.

Any relevant information from source documents regarding the SAE, e.g., hospital notes or discharge summaries, etc., must be summarized on the SAE form.

Follow-up information about a previously reported SAE must also be reported within 24 hours of receiving it. The sponsor's Global Drug Safety personnel may contact the investigator to obtain further information.

If the subject is hospitalized in a hospital other than that of the study site, it is the investigator's responsibility to contact this hospital to obtain all SAE-relevant information and documentation.

New SAEs occurring after the 30-day follow-up period or after the last visit of the PTOp period (whichever is the latest) must be reported to the sponsor's Global Drug Safety department within 24 hours of the investigator's knowledge of the event, **only** if considered by the investigator to be causally related to previous exposure to the study treatment.

9.4 Pregnancy

If a woman becomes pregnant while on study treatment, study treatment must be discontinued [see Section 5.1.10.1].

The investigator must counsel the subject and discuss the risks of continuing with the pregnancy and the possible effects on the fetus.

9.4.1 Reporting of pregnancy

Any pregnancy occurring in a female subject after signing of the ICF and up to 30 days following study treatment discontinuation must be reported to the sponsor's Global Drug Safety department within 24 hours of the investigator's knowledge of the event.

Any pregnancy occurring in the female partner of a male subject during the treatment period and up to the EOS visit or FU2 visit (whichever is first) must be reported to the sponsor's Global Drug Safety department within 24 hours of the investigator's knowledge of the event.

Pregnancies must be reported on the sponsor Pregnancy form, which is faxed to the sponsor's Global Drug Safety department (see contact details provided on the Pregnancy form).

The investigator must complete the Pregnancy form in English.

9.4.2 Follow-up of pregnancy

Any pregnancies must be followed-up to their conclusion and the outcome must be reported to the sponsor's Global Drug Safety department.

Any AE associated pregnancy of a female subject occurring up to the EOS visit must be reported on separate AE forms in the eCRF.

Any SAE occurring during the pregnancy must be reported on an SAE form as described in Section [9.3.2](#).

9.5 Reporting of study treatment overdose, misuse, abuse and medication errors

Study treatment overdose (defined as higher than the dose of study treatment prescribed), and study treatment errors will be reported as an AE when associated with signs or symptoms.

In addition, study treatment errors must be documented in the study drug log of the eCRF.

Misuse and abuse of the study treatment will be reported as an AE/SAE as determined.

9.6 Study safety monitoring

Study safety information (AEs, SAEs, laboratory values, ECGs, vital signs, and study-specific examinations as required) is monitored and reviewed on a continuous basis by the sponsor (in charge of ensuring subjects' safety as well as data quality).

The sponsor may request additional data pertaining to the diagnostic work-up of an AE or SAE (e.g., medical imaging, local laboratory values) for the purpose of monitoring safety. Such additional data may be shared with external experts.

10 STATISTICAL METHODS

10.1 Analysis sets

10.1.1 Screened Analysis Set

The Screened Analysis Set includes all subjects who have given informed consent to participate in the study and have a subject number.

10.1.2 Full Analysis Set

The Full Analysis Set (FAS) includes all subjects randomized to either lucerastat or placebo. In order to adhere to the intent-to-treat principle as much as possible:

- Subjects will be evaluated according to their assigned study treatment (not actual treatment received) and stratum information as recorded in the IRT system;
- Unless otherwise stated, all available efficacy data for the primary and secondary endpoints will be included in the analyses up to the planned analysis time point, regardless of study treatment discontinuation and/or switches to alternative FD treatments.

10.1.3 Modified Full Analysis Set

A modified FAS (mFAS) will be defined by including subjects from the FAS who took at least one dose of study treatment. As in the FAS, subjects will be analyzed based on the assigned study treatment.

10.1.4 Modified Full Analysis Set-gastrointestinal symptoms

The mFAS-gastrointestinal symptoms (mFAS-GIS) comprises all subjects from the mFAS who, during the 4 weeks prior to randomization, have experienced:

- Abdominal pain of moderate to severe intensity at baseline defined as an average abdominal pain intensity score ≥ 3 on a NRS-11 scale; and/or
- Diarrhea at baseline defined as having at least 1 stool of a BSS consistency Type 6 or 7 on at least 8 days.

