In the absence of regulatory guidelines specific to the development of treatment for FD at the time of the first version of the protocol, the methodology used in the study to assess the effect of lucerastat on GI symptoms has been based on the IBS [FDA 2012] and PRO [FDA 2009] guidance. According to the draft FDA guidance on development of drugs for FD treatment [FDA 2019], drug effectiveness can be established with the demonstration of clinically meaningful improvement in GI symptoms (abdominal pain, diarrhea, constipation).

Similarly to the neuropathic pain symptom, it is postulated that the potential effects of lucerastat on GI symptoms (abdominal pain and diarrhea) result from the reduction of Gb3 and lysoGb3 storage in the GI tract [see Section 1.3]. As for neuropathic pain, it is expected that the effect of lucerastat on GI symptoms would already be measurable at Month 6 in those subjects who had the corresponding symptom at baseline. Similar to neuropathic pain, GI symptoms may vary in frequency and intensity. Some subjects with FD describe a cyclic pattern of alternating diarrhea and constipation interspersed with periods of quiescence and normal bowel movements, making diagnosis and management particularly difficult [Keshav 2006]. Therefore, the baseline and Month 6 values will be derived from the subject's abdominal pain and diarrhea data collected over a period of 4 weeks [see Sections 10.2.2.1 and 10.2.2.2], i.e., a time duration reasonably long enough to capture a true reflection of the subject's score accounting for the variability of diarrhea and abdominal pain symptoms in subjects with FD.

Published IBS guidelines [FDA 2012, CHMP 2014] recommend assessing the efficacy of treatment on abdominal pain intensity in subjects with moderate to severe abdominal pain by using uni-dimensional pain scales (e.g., NRS-11) that ask subjects to rate their abdominal pain at its worst in the last 24 hours on a daily basis. This is also in line with the recommendation from the IMMPACT consensus conference [Dworkin 2005]. The criteria used to define a subject with moderate to severe abdominal pain at baseline are consistent with the published IBS guidelines [FDA 2012]. The abdominal pain intensity rating scale used in this study [see Section 7.2.2.2.2] has been previously tested in a cognitive debriefing / usability testing study conducted in subjects with FD.

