10.3.3 Analysis of the secondary efficacy variables

10.3.3.1 *Change from baseline to Month 6 in the 11-point numerical rating scale score of “abdominal pain at its worst in the last 24 hours” in subjects with gastrointestinal symptoms at baseline*

This endpoint will be analyzed using the mFAS-GIS. All available data will be used regardless of occurrence of ICEs such as premature treatment discontinuation or changes in background medication.

Missing data will be imputed applying a control-based MI assuming MNAR using the CR approach, as described for the primary endpoint in Section 10.3.2.2.

An ANCOVA model will be used to analyze this endpoint on each imputed dataset. The following terms will be included in the model: baseline value, the two stratification factors (sex and ERT treatment status at screening), and the treatment group.

Uncertainty in the imputations will be reflected appropriately in the analysis by combining the results on each imputed dataset using Rubin’s methodology [Rubin 1987].

The mean difference in changes from baseline to Month 6 between lucerastat and placebo together with its two-sided 95% CI and p-value will be reported.

To explore the robustness of inferences from the main analysis described above to deviations from its underlying assumptions regarding the nature of missing data, a control-based MI assuming MNAR using the J2R approach [Carpenter 2013] will be applied, as described in Section 10.3.2.4.

A supportive analysis using an MMRM approach will be conducted to characterize the treatment effect over time such that the monthly average NRS-11 scores will be analyzed on all available data from all monthly visits without replacement of missing values.

The model will enable:

- Estimation of the treatment difference (lucerastat minus placebo) in the mean changes from baseline to Month 6 along with the corresponding 95% CIs;
- Characterization of the patterns of change over time in the mean change from baseline in “abdominal pain at its worst in the last 24 hours” by treatment group.

A supportive dichotomous responder analysis will be conducted using the CMH test as described in Section 10.3.2.5. Response to study treatment on abdominal pain will be defined as a reduction from baseline to Month 6 of at least 50% in the NRS-11 score (“abdominal pain at its worst in the last 24 hours”) in subjects with abdominal pain of moderate to severe intensity at baseline.

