10.5 Sample size

The planned sample size for this study is 99 subjects using a 2:1 allocation ratio (66 lucerastat, 33 placebo) and is primarily based on a test for the mean difference between lucerastat and placebo in the change from baseline to Month 6 in the “modified” BPI-SF3 score.

The sample size calculation for the primary endpoint analysis is based on the following assumptions: a clinically relevant difference of 2 points on the 11-point scale (0–10) between lucerastat and placebo, a corresponding SD of 3 points, a two-sided type I error of 5%, and equal group variances. These assumptions come from an expected mean decrease from baseline to Month 6 in BPI-SF3 in the lucerastat group of 1.0-1.5 (2-year data for subjects on ERT; [Hoffmann 2007b]), and an expected mean increase from baseline in the placebo group of approximately 0.5 to 1.0 [Weidemann 2014]. Following these assumptions 99 subjects will provide a power of 87.2% to detect a treatment difference between lucerastat and placebo on the primary endpoint. The calculations were conducted using East 6.5 based on a two-sided t-test for independent samples.

For the analysis of the secondary efficacy endpoints, it is expected that about 70% of the randomized subjects will be included in the mFAS-GIS. Under this assumption the assessment of the secondary endpoints may be carried out on about 69 subjects (approximately 46 on lucerastat and 23 on placebo). Little is known from the literature on the expected effect size that might be observed for these endpoints however a reasonable treatment effect on the abdominal pain endpoint (NRS-11) could be a difference (delta) of

1.5–2.5 points on that scale with an expected variability (SD) in the region of 2.5–3.5. For illustration purposes, and in absence of missing data, the power to detect such an effect with this sample size for the analysis of a continuous endpoint is shown in [Table 7](#).

Table 7 Power to detect a treatment difference for continuous secondary endpoints analyzed on the mFAS-GIS for a range of deltas and SDs (n = 69 subjects)

alpha = 5% two-sided			
delta	SD = 2.5	SD = 3.0	SD = 3.5
1.5	63.9%	48.8%	38.0%
2.0	87.0%	73.0%	59.7%
2.5	97.1%	89.5%	78.7%

SD = standard deviation.

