#### 15.3.1 Change from baseline to Month 6 in the NRS-11 score of “abdominal pain at its worst in the last 24 hours” in subjects with GI symptoms at baseline

The same approach (CR MI + ANCOVA as main analysis with MAR MI and J2R MI + ANCOVA as sensitivity analyses) as described in Sections 15.2.3 and 15.2.4 will be used to analyze this endpoint on the mFAS-GIS. Subjects with the baseline value missing will be excluded from this analysis.

Subgroup analyses will be performed similarly to those described in Section 15.2.6 by including the respective subgroup and subgroup by treatment interaction in the ANCOVA.

The following supportive analyses will be performed:

- The same approach (CMH test) as described in Section 15.2.5.1 will be used to analyze a response variable (yes/no) defined as a reduction from baseline to Month 6 of at least 50% in the NRS-11 score.
- The same approach (MMRM) as described in Section 15.2.5.5 will be used to characterize the treatment effect over time.

Patterns of missingness will be summarized as described in Section 15.2.2. An eCDF plot of the absolute change from baseline to Month 6 by treatment arms will be provided as well.

Descriptive summary statistics of the absolute values and changes from baseline will be provided on the mFAS-GIS and the mFAS.

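### SAP 15.3.1 drops, without declaring it, the protocol's limit of the abdominal-pain responder analysis to subjects who had abdominal pain at baseline, and no planned comparison then estimates the pain effect in those subjects

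*Protocol*

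**What the plan says.** - **The set.** Protocol 10.1.4 and SAP 4.1.4 define the mFAS-GIS by two criteria joined by and/or. One is "Abdominal pain of moderate to severe intensity at baseline defined as an average abdominal pain intensity score" of at least 3 on the 0–10 scale; the other is a Type 6 or 7 stool on at least 8 days. Both refer to the 4 weeks before randomization. Both GI secondary endpoints are tested on the whole set (protocol 10.3.3.1 and 10.3.3.2; SAP 15.3.1 and 15.3.2).
- **The rationale.** Protocol 6.6.2 expects the effect on GI symptoms to be "measurable at Month 6 in those subjects who had the corresponding symptom at baseline".
- **Responders, protocol.** Section 10.3.3.1 plans a supportive CMH analysis of a 50% reduction in the pain score "in subjects with abdominal pain of moderate to severe intensity at baseline".
- **Responders, SAP.** Section 15.3.1 gives a response variable "defined as a reduction from baseline to Month 6 of at least 50% in the NRS-11 score" and names no sub-population. Section 15.3.2 defines the diarrhea responder only for subjects who had diarrhea at baseline.
- **Declared changes.** SAP Section 20 covers subgroup definitions only.
- **Sample size.** Protocol 10.5 states that "it is expected that about 70% of the randomized subjects will be included in the mFAS-GIS", about 69 subjects (46 and 23), and Table 7 gives power for that number.

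**The concern.** Two things follow from the and/or set.

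First, without the protocol's restriction the abdominal-pain responder analysis takes in diarrhea-only subjects, whose average pain was below 3. A percentage criterion loses meaning as the baseline falls, so the responder proportions would partly reflect noise at low baselines. The SAP also departs here from the protocol without saying so, and treats the two GI endpoints differently for no stated reason.

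Second, SAP Section 6 has no subgroup for baseline abdominal pain or baseline diarrhea. With the restriction gone, no planned comparison estimates the pain effect in subjects who had the pain. For diarrhea, only the binary responder analysis does so. If the pooled result is weak, a reader cannot tell absence of effect from an effect averaged over subjects without the symptom, although 6.6.2 places the expected effect in those who have it.

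**Working it through.** **1. Responder definition, side by side.**

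| | Abdominal pain | Diarrhea |
|---|---|---|
| Protocol | Restricted to baseline pain (10.3.3.1) | Same responder approach applied (10.3.3.2) |
| SAP | No restriction (15.3.1) | Restricted to baseline diarrhea (15.3.2) |
| Listed in SAP Section 20 | No | Not applicable |

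**2. What a 50% fall requires.** The required fall is 0.5 × baseline score. At baseline 3 (the entry criterion) it is 1.5 points; at 1 it is 0.5; at 0.5 it is 0.25. At 0 no fall is possible. The criterion erodes gradually below 3 and becomes empty near 0.

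**3. Table 7 reproduced.** Inputs from protocol 10.5: groups of 46 and 23, two-sided alpha 5%, delta 2.0, SD 3.0. The noncentrality is 2.0 / (3.0 × √(1/46 + 1/23)) = 2.61 with 67 degrees of freedom. Noncentral-t power is 73.0%, as stated. The other eight cells also agree within 0.1 point. Table 7 applies the full delta to all 69 subjects.

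**4. What pooling could do to abdominal-pain power.** Let f be the share of the set with abdominal pain at baseline, with delta 2 and SD 3 in those subjects. Let e and s be the effect and SD in the rest. The documents give none of f, e or s, so all three are assumptions.

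- Pooled effect = 2f + e(1 − f)
- Pooled SD ≈ √(9f + s²(1 − f))
- Symptomatic subset: effect 2, SD 3, groups 46f and 23f

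At f = 2/3:

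| Rest: SD s, effect e | Pooled effect | Pooled SD | Pooled power (46/23) |
|---|---|---|---|
| 3, 0 | 1.33 | 3.00 | 40% |
| 1, 0 | 1.33 | 2.52 | 53% |
| 2, 0.5 | 1.50 | 2.71 | 57% |
| 1.5, 0.5 | 1.50 | 2.60 | 61% |
| 1, 0.5 | 1.50 | 2.52 | 63% |

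The symptomatic subset (30.7 and 15.3) has power 55.0%; whole numbers, 31 and 15, give 54.5%.

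The first row varied over f (SD 3, zero effect in the rest):

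| f | Pooled power | Subset power |
|---|---|---|
| 0.9 | 63.9% | 68.3% |
| 0.7 | 43.7% | 57.1% |
| 0.5 | 25.1% | 43.3% |

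With s = 1 and zero effect in the rest, pooled power is 55.7% at f = 0.7 and 40.8% at f = 0.5, close to the subset.

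**5. Actual enrolment.** SAP Section 2 reports 118 randomized, and 70% of 118 is about 83. With 82 subjects (55 and 27) and f = 2/3, the first-row case gives 46% pooled against 62% in the subset.

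**6. Limit of the figures.** The diarrhea endpoint is tested by stratified rank ANCOVA with a win ratio as estimate. These t-test figures do not carry over to it.

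**The case against.** The and/or set is declared and consistent. The secondary objective (protocol 2.2), the endpoints (6.1.2), estimands #2 and #3 (6.1.3) and the analysis set all refer to subjects with GI symptoms at baseline. Protocol 6.6.2 also describes symptoms that come and go, so a subject below one cut-off in a single 4-week window need not be free of that symptom. Preferring a symptom-specific confirmatory set is a design preference. This stands, and the set should not change.

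A reader might infer two stronger claims: that the protocol expects an effect only in subjects with the matching symptom, and that the third and fourth confirmatory tests therefore lose power. The documents support neither. Section 6.6.2 says where an effect is expected and does not exclude one elsewhere. A diarrhea-only subject may have average pain just under 3, and a pain-only subject may have up to 7 diarrhea days in 28, so both can improve. Prevented worsening could also produce a difference. With low variability and a small effect in the rest, the pooled set has more power than the subset. Both main analyses already adjust for baseline.

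Finally, the responder analysis is supportive and carries no alpha. That is true and limits the consequence. It does not explain why the SAP departs from the protocol for one GI endpoint and not the other.

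**Conclusion.** The undeclared omission in SAP 15.3.1 is established from the text and rests on no assumption. It affects a supportive analysis, where it admits subjects with average pain below 3 for whom the 50% criterion means little. The absence of a planned comparison for abdominal pain in subjects with that symptom is likewise established, from SAP Sections 6 and 15.3.1.

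A loss of confirmatory power is possible but not established. If subjects without the symptom respond less, the mean effect is diluted; by how much depends on their share and their effect, and the power consequence also on their SD. At a two-thirds share, pooled power for abdominal pain lies between about 40% and about 63% over the cases tried, on either side of about 55% in the subset. Nothing can be said numerically about the diarrhea test.

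**What to change.** - In SAP 15.3.1, restore the protocol's restriction of the 50% responder analysis to subjects with average baseline abdominal pain of 3 or more. If the wider population is intended, list it in Section 20 with a reason.
- Pre-specify, as supportive and outside the alpha-controlled sequence, the abdominal-pain ANCOVA in subjects with abdominal pain at baseline and the diarrhea rank ANCOVA with win ratio in subjects with diarrhea at baseline.
- Leave the mFAS-GIS as the confirmatory population, and leave the estimands and testing order unchanged.

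The cost is SAP wording before unblinding and two extra tables. The subsets are smaller, about 46 subjects at a two-thirds share of 69, so their estimates will be less precise. They help interpretation and do not restore confirmatory power.
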